7 INVESTIGATIONAL PLAN

7.1 Study Design and Plan-Description

The study is an open-label, randomized, controlled, two (2) armed, multicenter, phase II study. Intermediate- and high-risk mRCC patients according to Heng criteria are eligible for participation [4]. Stratified randomization based on Heng-risk categories applies. The patients are randomized in a consecutive order to one (1) of the following two (2) treatment arms when eligibility has been confirmed;

- (i) Two (2) doses of Intuvax (10×10^6 DCs) administered intratumorally into the primary tumor 14 ± 3 days apart followed by nephrectomy at least three (3) days after the second vaccine dose.

AND

Sunitinib treatment initiated five (5) to eight (8) weeks after nephrectomy, administered dose in accordance with the SmPC/USPI.

- (ii) Sunitinib treatment initiated five (5) to eight (8) weeks after nephrectomy, administered dose in accordance with the SmPC/USPI.

The estimated number of patients to be randomized in the study is around 90. The patients will be randomized in a 2:1 (vaccine treatment arm [i]:control treatment arm [ii]) ratio. Stratification will be done at randomization for intermediate- and high-risk patients.

Patients randomized to treatment arm (i) are scheduled for 12 study visits and patients randomized to treatment arm (ii) are scheduled for 10 study visits during a study period of 78 weeks, see list below and *Figure 1*. In addition, all patients being exposed to any of the Investigational Medicinal Products (IMPs) will have a safety evaluation done for collection of SAEs up to 30 days after last dose of IMP administered in the study. The following visits apply for the two (2) patient populations:

- Screening Visit (Screening)
- Vaccination 1 Visit (Vacc1), applicable for patients randomized to treatment arm (i)
- Vaccination 2 Visit (Vacc2), applicable for patients randomized to treatment arm (i)
- Nephrectomy Visit (Nephrectomy)
- Sunitinib Start Visit (Sun-Start), five (5) to eight (8) weeks after Nephrectomy
- Sunitinib Follow-up Visits (SFU[6W] and SFU[12W]), every 6 weeks for 12 weeks or until locally CT-verified PD whichever occurs first
- Sunitinib Follow-up Visits (SFU[24W], SFU[36W], SFU[48W], and SFU[60W]), every 12 weeks until End-of study or until locally CT-verified PD whichever occurs first
- End-of-Study Visit (End-of-Study)

[figure not shown]

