8.5 Removal of Patients from Therapy or Assessment

Patients are free to discontinue their participation in the study at any time. Withdrawal from the study will not affect or prejudice the patient's further care or treatment. Patients may be withdrawn from study treatment and assessments at any time, if deemed necessary by the Investigator.

Patients who discontinue treatment with Intuvax and/or sunitinib for safety reasons (including DLT, see *Section 11.5*) or due to concomitant medication (*Section 9.6*) will not necessarily be considered withdrawn from the study unless there are other reasons for withdrawal. They should return for all following visits and assessments until PD.

Examples of reasons for withdrawal of patients from this study are:

- Progressive disease on sunitinib treatment
- Screening failure
- The decision of a patient to withdraw from the study (i.e. if the patient withdraws informed consent)
- Administration of concomitant medication prohibited by this protocol, *Section 9.6*
- Pregnancy
- Patient is lost to follow-up
- RCC diagnosis is not confirmed by histological findings from the biopsy collected at nephrectomy or, if applicable, from confirmatory pre-study treatment diagnostic biopsy

The reason and date the patient is withdrawn from the study and subsequent planned replacement therapy will be documented in the electronic case report form (eCRF).

All patients that have received IMP must have safety evaluations for 30 days after the last dose of IMP, *Section 11.2*.

If a patient is withdrawn from further assessments, the Investigator should attempt to complete all discharge procedures, i.e. End-of Study Visit. All AEs should be followed up according to *Section 11.2*.

If a patient is withdrawn from the study, all data collected until the time of withdrawal will be used in the analyses.

Survival data (including post-study survival data if applicable) will be collected and analyzed for all patients withdrawn from the study, *Section 11.3*.

Patients randomized to Intuvax who withdraw from the study before administration of the first dose of Intuvax will be considered screening failures. Patients randomized to sunitinib alone who withdraw from the study before any assessments made at the first visit following Screening will be considered screening failures.

Only patients considered screening failures will be replaced.

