10.2.2 Secondary Efficacy Variables and Assessments

10.2.2.1 Progression Free Survival (PFS) from Start of Sunitinib

PFS from start of sunitinib is defined as time from Sunitinib Start Visit to PD or death following sunitinib initiation from any cause, whichever occurred first. PFS from start of sunitinib will be evaluated per stratum and in total from the two (2) different treatment arms as a secondary efficacy variable.

Note: For intermediate-risk patients included in the trial according to protocol versions before version Final 4.0, sunitinib treatment did not have to be initiated at a fixed time point. For these patients, the first imaging assessment after nephrectomy will be used as baseline for evaluation of PFS, irrespective of whether or not the imaging assessment coincided with sunitinib treatment start. Further details will be provided in the Statistical Analysis Plan (SAP).

10.2.2.2 Objective Response Rate and Duration of Response and Stable Disease from Start of Sunitinib

Evaluation of tumor response is based on centrally assessed CT scans, *Section 10.4.3*, according to the RECIST 1.1 guideline [1].

Definitions - RECIST v1.1

a) Measurable Disease

The presence of at least one (1) measurable lesion. If the measurable disease is restricted to a solitary lesion, its neoplastic nature should be confirmed by cytology/histology. The same measurable and non-measurable lesions will be followed by RECIST v1.1. Disease progression will be determined using RECIST v1.1 criteria.

- Malignant lymph nodes

To be considered pathologically enlarged and measurable, a lymph node must be >15 mm in short axis when assessed by CT scan (CT scan slice thickness

recommended to be no greater than 5 mm). At baseline and in follow-up, only the short axis will be measured and followed.

- **Baseline documentation of “Target” and “Non-Target” lesions**
All measurable lesions up to a maximum of 2 lesions per organ and 5 lesions in total, representative of all involved organs, should be identified as target lesions and recorded and measured at baseline.

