6.3.6 Secondary Efficacy Analyses

PFS from start of sunitinib according to RECIST 1.1

PFS from start of sunitinib treatment will be derived as date whichever occurred first of any cause of death or date for first tumor progression (which is date for centrally assessed CT performed, according to RECIST 1.1) minus date for start of sunitinib treatment plus 1 day.

For the analysis of PFS only deaths occurring before end-of-trial will be accounted for in the analysis.

Analysis of PFS will be evaluated the following way:

Survival functions will be displayed graphically using Kaplan-Meier plots, and life table statistics will be produced including summaries of number of events and censored observations. Estimates of cumulative 25%, 50% (median) and 75% percentiles of survival with corresponding 95% confidence intervals will be calculated.

Comparison between Intuvax+sunitinib, vs. sunitinib alone will be done using a stratified log-rank test (controlling for strata intermediate/high risk), separate analyses will also be done by strata.

With protocol versions before version 4.0, intermediate risk patients did not have to initiate treatment with sunitinib at a fixed time point according to the visit schedule. Consequently some patients were never started on sunitinib, and in some cases sunitinib treatment was initiated at a later time point. The sunitinib start date constitutes the baseline time point for PFS according to protocol version 4.0 and after. In the analyses, patients who either had a delay or never started sunitinib will be included under the assumption that sunitinib treatment would have been initiated according to the final design, the date of the visit following the nephrectomy visit will be used as baseline.

Another issue that will be considered in the analysis is that some patients may have been discontinued based on general clinical disease progression as evaluated by investigator from symptoms/signs of disease, rather than based on a PD according to RECIST 1.1. For the analysis such cases will be handled strictly based on the RECIST 1.1 evaluation, thus if a patient is withdrawn without a CT confirmed PD the subject will be censored at last CT

Analyses will be based on FAS and repeated for separately by strata..

Proportion of Objective Response Rate (ORR) and Disease Control Rate (DCR) from start of sunitinib

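### SAP 6.3.6 leaves open whether a death after withdrawal for clinical progression is a PFS event or is lost to censoring at the last CT; the protocol counts it

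*SAP*

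**What the plan says.** Protocol 10.2.2.1 defines PFS as "time from Sunitinib Start Visit to PD or death following sunitinib initiation from any cause, whichever occurred first". It sets no cut-off at withdrawal. The endpoint in Protocol 10.1 is PFS by RECIST 1.1, and Protocol 10.4.3 bases it on central reads made without knowledge of the arm.

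SAP 6.3.6 starts in the same way. It takes the "date whichever occurred first of any cause of death or date for first tumor progression", with progression dated by the centrally assessed CT. Two further sentences narrow this:

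- On deaths: "only deaths occurring before end-of-trial will be accounted for in the analysis".
- On withdrawals: the SAP expects that "some patients may have been discontinued based on general clinical disease progression as evaluated by investigator from symptoms/signs of disease", without a RECIST PD, and rules that "thus if a patient is withdrawn without a CT confirmed PD the subject will be censored at last CT".

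Death dates are available for these patients. Protocol 8.5 states: "Survival data (including post-study survival data if applicable) will be collected and analyzed for all patients withdrawn from the study". Protocol 11.3 adds that survival information obtained after a patient's End-of-Study Visit is kept in the safety database and not in the clinical database.

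The readable part of SAP 6.1 does not list the handling of these deaths as a change from the protocol (some bullets there are redacted). The readable SAP plans no PFS sensitivity analysis on this point.

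**The concern.** There are two separate problems.

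First, the SAP does not decide what happens to a patient who is withdrawn for clinical progression and then dies. Two programmers could follow the same text and produce different PFS results. Because later deaths sit only in the safety database, an analysis run from the clinical database would leave them out by default.

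Second, if the withdrawal sentence is applied as written, the censoring is informative. These patients leave because they are judged to be failing. Kaplan-Meier and log-rank methods nevertheless give them the outlook of patients who are still being scanned. The trial is open-label, so that judgement is made with the arm known. Central blinded reading cannot repair a scan that was never done.

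At stake are the PFS medians in each arm and, if such withdrawals are more frequent in one arm, the comparison itself.

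**Working it through.** **Step 1. The texts side by side.** Take an illustrative patient with a last CT at week 12 after sunitinib start, clinical withdrawal at week 13 and death at week 17. The term end-of-trial could be read in two ways. Protocol 7.5 defines the end of study at trial level (last patient's last visit or safety evaluation). SAP 6.6 speaks of an end-of-trial visit for an individual patient who withdraws early.

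| Text applied | Outcome |
|---|---|
| Protocol 10.2.2.1 | Event at week 17 |
| SAP death sentence, trial-level end | Event at week 17 |
| SAP death sentence, patient-level end | Death not counted |
| SAP withdrawal sentence | Censored at week 12 |

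With a trial-level end the SAP contradicts itself. With a patient-level end its sentences agree, and together they depart from the protocol.

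**Step 2. Expected size.** The documents give no PFS assumption, event count or withdrawal rate, so there is no planned figure to reproduce. Suppose failure is exponential and a share s of failures is clinical and censored. The hazard that remains visible is (1 − s) times the true one. Hence:

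- The median is inflated by 1/(1 − s): 1/0.9 = 1.11, 1/0.8 = 1.25 and 1/0.7 = 1.43 for s = 10%, 20% and 30%.
- With identical true hazards, the apparent hazard ratio is (1 − s₁)/(1 − s₀). For 30% v 10% it is 0.7/0.9 = 0.78; for 10% v 30% it is 0.9/0.7 = 1.29; for equal shares it is 1.00.

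**Step 3. Simulation on the planned scan schedule.** Scans are "every 6 weeks for 12 weeks or until locally CT-verified PD whichever occurs first", then every 12 weeks. Both simulations assume exponential failure with a median of 8 months and no true difference between arms.

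- A: large samples; median 2 months from clinical failure to death; scans at weeks 6, 12, 24, 36, 48, 60 and 66.
- B: 60 v 30 patients, 1,500 trials per scenario, unstratified log-rank; median 13 weeks from withdrawal to death; scans to week 60.

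Neither simulation includes a discharge CT in the results below.

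| PFS rule | A: 12-month PFS, s = 20% | A: 12-month PFS, s = 30% | A: HR, 30% v 10% | B: HR, 30% v 10% (rejection) | B: HR, 10% v 30% (rejection) | B: HR, 20% v 20% (rejection) |
|---|---|---|---|---|---|---|
| Censor at last CT | 45% | 49% | 0.81 | 0.77 (13.5%) | 1.28 (11.9%) | 1.00 (5.3%) |
| Count later deaths | 40% | 41% | 0.97 | 0.92 (5.1%) | 1.08 (5.5%) | 1.00 (4.3%) |
| Clinical progression is an event | 38% | 37% | 1.03 | 1.03 (4.8%) | 0.96 (5.9%) | 1.00 (4.1%) |

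Rejection is at a nominal two-sided 5%; its simulation standard error near 5% is √(0.05 × 0.95/1,500) = 0.6 percentage points. At smaller imbalances the effect shrinks: censoring at the last CT gives 0.87 for 25% v 10% in A and 0.87 for 20% v 10% in B.

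PFS events per 90 patients in B, for s = 10/20/30%, are 57/51/44 with censoring at the last CT, 61/60/58 with deaths counted and 63/63/62 with clinical progression as an event. At 20%, 60 − 51 = 9 deaths per 90 patients are dropped.

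**Step 4. No post-baseline CT.** Protocol 7.2.1.5 lets the Sun-Start CT fall anywhere in the window of 5 to 8 weeks after nephrectomy, so it may precede sunitinib start by up to 3 weeks. The SAP time is date minus start plus 1 day. A patient who leaves before the week-6 scan with no discharge CT is therefore censored at day 1 if the baseline CT was on the start day, and at −21 + 1 = −20 days at the extreme. No rule covers times of zero or less. In B, across true medians of 5, 8 and 11 months, 0.7% to 5.3% of patients fall in this group, or about 0.6 to 4.8 of 90.

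**The case against.** The strongest reply is that the SAP already makes death from any cause an event, so the withdrawal sentence can be read as applying only to patients with no recorded death. That reading is possible, and for this reason the text does not support saying that the SAP plainly orders such deaths to be ignored. But the SAP never states the precedence, and it limits deaths by a term that it does not define.

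Four further points have weight:

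- **RECIST-only PFS is what the protocol specifies.** Keeping arm-aware clinical judgement out of the main analysis of an open-label trial is sound. A reader might infer that clinical progression should have been a PFS event; the documents do not support that.
- **TTP partly covers the gap.** SAP 6.3.6 counts clinical progression as a TTP event and analyses TTP by the same methods as PFS. But TTP excludes deaths, so no readable analysis combines RECIST PD, clinical progression and death.
- **A discharge CT is expected.** Protocol 8.5 asks for an attempt at the End-of-Study Visit on withdrawal, 9.6 asks for that visit before a change of systemic therapy, and 7.2.1.7 includes imaging in it. Protocol 10.2.2.2 also asks for efforts to document objective progression after treatment stops. A reader might infer that all the earliest failures contribute no PFS time; that is true only of those with neither a post-baseline nor a discharge CT.
- **Between-arm bias needs unequal withdrawal shares.** Nothing in the documents says that they differ, or in which direction.

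**Conclusion.** The point stands as an unreconciled conflict in the PFS rules of SAP 6.3.6. On the literal reading of the withdrawal sentence, it is also a departure from Protocol 10.2.2.1 that the readable SAP 6.1 does not list. The censoring is informative and overstates PFS in each arm.

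The size is unknown. Under the assumed shares of 30% v 10% with no true difference, the apparent hazard ratio is 0.77 to 0.81, against 0.92 to 0.97 with deaths counted. With equal shares there is no between-arm bias, and the harm is to the medians. These figures rest wholly on assumed failure times, withdrawal shares and survival after withdrawal. They show what the rule can do, not what it did.

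A reader might infer that the rule favours Intuvax. The documents do not support that: the bias favours whichever arm has more such withdrawals. PFS is a secondary endpoint and all testing is exploratory (Protocol 12.1.3, SAP 6.4), so this should be fixed but does not threaten the primary analysis.

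**What to change.** Change SAP 6.3.6 before database lock:

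1. State that death from any cause after sunitinib start (or after the substitute baseline for patients enrolled before protocol version 4.0) is a PFS event and takes precedence over censoring at withdrawal, unless centrally read PD came first.
2. Define end-of-trial as a single trial-level cut-off date. Take deaths after a patient's End-of-Study Visit from the safety database, as is done for OS.
3. Where there is no post-baseline CT, or the last CT precedes sunitinib start, censor at day 1.
4. Keep centrally read RECIST PFS as the main analysis. Add one sensitivity analysis that counts RECIST PD, withdrawal for clinical progression (on its date) and death as events.
5. Report the number of withdrawals for clinical progression without CT-confirmed PD, by arm and stratum.

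A time limit on deaths after the last CT is not the better route here. A 14-week limit, for example, gives a hazard ratio of 0.92 in simulation A at 30% v 10%, against 0.97 with no limit, and it too departs from the protocol definition.

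Cost: SAP wording, a merge of safety-database death dates and one repeat of the PFS analysis. Reported PFS becomes slightly shorter. Some deaths will count after a gap without scans, while patients still alive remain censored at their last CT. The sensitivity analysis will include investigator-judged events.

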7.2.1.6 SFU[6W], SFU[12W], SFU[24W], SFU[36W], SFU[48W], and SFU[60W]

These visits are applicable for all patients unless locally CT-verified PD occurs. In case of PD this visit should be considered the End-of-Study Visit.

If SFU[60W] is scheduled ≥ 76 weeks since Screening this visit should be considered the End-of-Study Visit, *Section 7.2.1.7*.

TIME WINDOWS:

SFU[6W]: 6 weeks (± 7 days) after Sun-Start Visit
SFU[12W]: 12 weeks (± 7 days) after Sun-Start Visit
SFU[24W]: 24 weeks (± 7 days) after Sun-Start Visit
SFU[36W]: 36 weeks (± 7 days) after Sun-Start Visit
SFU[48W]: 48 weeks (± 7 days) after Sun-Start Visit
SFU[60W]: 60 weeks (± 7 days) after Sun-Start Visit

NB: The CT/MRI scans do not have to be done the very same day as the corresponding study visits. However, each CT/MRI scan has to be done within the specified time window for the corresponding visit.

ACTIVITIES AND ASSESSMENTS:

The same activities and assessments will be done at these visits as was done on Sun-Start Visit except for auto- and alloimmunization, *Section 7.2.1.5*. In addition to dispense of sunitinib, the site personnel will collect unused and empty sunitinib packages (distributed at the previous visit) from the patient for drug accountability, *Section 9.1.4*.

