
Incomplete Response/ Stable Disease (SD)	Persistence of one or more non-target lesion(s) or/and maintenance of tumor marker level above the normal limits
------------------------------------------	------------------------------------------------------------------------------------------------------------------

^a Although a clear progression of “non-target” lesions only is exceptional, the opinion of the treating physician should prevail in such circumstances, and the progression status should be confirmed at a later time by the Investigator.

Evaluation of Best Overall Response

The best overall response is the best response recorded from the start of the treatment Sunitinib until disease progression/recurrence (taking as reference for PD the smallest measurements recorded since the treatment started). In general, the subject's best response assignment will depend on the achievement of the measurement criteria.

Table 6 Evaluation of Best Overall Response

Target Lesions	Non-Target Lesions	New Lesion	Overall response
CR	CR	No	CR
CR	Incomplete response/SD	No	PR
PR	Non-PD	No	PR
SD	Non-PD	No	SD
PD	Any	Yes or No	PD
Any	PD	Yes or No	PD
Any	Any	Yes	PD

Subjects with a global deterioration of health status requiring discontinuation of treatment without objective evidence of disease progression at that time should be classified as having “symptomatic deterioration.” Every effort should be made to document the objective progression even after discontinuation of treatment.

Note: For intermediate-risk patients included in the trial according to protocol versions before version Final 4.0, the first imaging assessment after nephrectomy will be used as baseline for evaluation of best overall response, irrespective of whether or not the imaging assessment coincided with sunitinib treatment start. Further details will be provided in the SAP.

Definitions for Response Evaluation

a) Confirmation of Response

To be assigned a status of complete or partial response, changes in tumor measurements do not need to be confirmed by repeat assessments after the criteria for response are first met.

b) Response rate

To be evaluated as the highest observed score of response during the study after randomisation in the ordinal categories of CR, PR, PD, SD and “Not evaluable”. The response rate will be evaluated according to the Schedule of Study Events, *Section 7.2.1*.

c) Objective response

Is defined as the proportion of patients with CR and PR.

d) Disease control rate (DCR)

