- Sunitinib Start Visit (Sun-Start), five (5) to eight (8) weeks after Nephrectomy
- Sunitinib Follow-up Visits (SFU[6W] and SFU[12W]), every 6 weeks for 12 weeks or until locally CT-verified PD whichever occurs first
- Sunitinib Follow-up Visits (SFU[24W], SFU[36W], SFU[48W], and SFU[60W]), every 12 weeks until End-of study or until locally CT-verified PD whichever occurs first
- End-of-Study Visit (End-of-Study)

The above described visits are applicable to all randomized subjects after and including protocol version 4.0. Subjects entering the trial corresponding to protocol versions prior to this, were included following a visit pattern that was different for high and intermediate risk patients. Following this design intermediate risk subjects would only start sunitinib treatment after confirmed PD.

At the two (2) Vaccination Visits, the patients are be administered Intuvax (10 x10⁶ DCs) intratumorally in the viable part of their primary tumor. Vaccine from the same batch (i.e. the same donor) is be used at both occasions. The patient stay at the clinic at least four (4) hours after vaccination. Nephrectomy is done at least 3 days after the second vaccination and maximum 63 days after Screening. Sunitinib treatment is initiated five (5) to eight (8) weeks after nephrectomy, administered dose is in accordance with the SmPC/USPI.

All patients are encouraged to contact the clinic in between study visits if they experience adverse events (AEs) or have any concerns. If follow-up of any symptoms is needed between the planned visits, the patient are scheduled for a visit as soon as possible and applicable assessments are performed.

A diagram of the study design is provided in Figure 1, and a flow chart what all assessments to be conducted per visit are provided in Tables 1 and 2.

Post-study survival data (either patient alive or date of death) will be collected.

[figure not shown]

Figure 1 Overall Study Design

Table 1 Study Flow Chart

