Proportion of ORR from start of sunitinib treatment will be derived as the proportion of patients with the individual's best overall response scored as "CR" or "PR" (using RECIST 1.1) across all time points from first visit six (6) weeks after sunitinib treatment, to end-of-study visit. Similarly, DCR will be derived as proportion of patients with best overall response scored as "CR", "PR" or "SD".

ORR and DCR will be summarised and comparison of treatment groups will be made using the Cochran Mantel-Haenzel test, adjusting for strata.

Duration of response will be derived only for patients meeting the ORR definition CR or PR, at least once, as the date of the first occurrence of PD or death minus the date at which the CR or PR was first observed, plus 1 day. Patients without an occurrence of a PD or death after CR or PR will contribute with the time up till last tumor assessment. Data will be summarised descriptively.

Duration of clinical benefit will be derived only for patients meeting the DCR definition CR, PR or SD at least once, as the date of the first occurrence of PD or death minus the date at which the CR, PR or SD was first observed, plus 1 day. Patients without an occurrence of a PD or death after CR, PR or SD will contribute with the time up till last tumor assessment. Data will be summarised descriptively.

The duration of stable disease is calculated for only those patients who exhibited a best response of stable disease response and will be calculated as the date for the first SD

response to the date of the first observed progression of disease or death before end of trial, if the death was due to disease progression (whichever comes first) plus 1 day. Data will be summarised descriptively.

Response rate from Sunitinib Start Visit

Evaluation of response rate, based on CT and according to the RECIST 1.1 guideline, from Sunitinib Start Visit will be based on the subpopulation from FAS who have been exposed to at least one dose of sunitinib. Number of patients with CR, PR, PD, and SD after start of sunitinib will be summarized using the underlying ordinal scale.

Waterfall charts will be used to display the percent change in target lesion tumour dimension vs best overall response and Two types of Swimmer plots will be created, one with bars showing time from randomization and one from sunitinib start. In these events for progressive disease, end of trial and vital status will be indicated.

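### The SAP scores best overall response without a stop at progression; this matters when central PD precedes local PD and for intermediate-risk patients enrolled before protocol version 4.0

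*SAP*

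**What the plan says.** **SAP 6.3.6** counts a patient towards ORR if best overall response is CR or PR by RECIST 1.1, and towards DCR if it is CR, PR or SD. The ORR window runs "across all time points from first visit six (6) weeks after sunitinib treatment, to end-of-study visit", and DCR is derived in the same way. Nothing in the sentence ends scoring at PD.

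**Protocol 10.2.2.2** does end it: "The best overall response is the best response recorded from the start of the treatment Sunitinib until disease progression/recurrence". The same section also defines a response rate with no such stop: "To be evaluated as the highest observed score of response during the study after randomisation".

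**Visits.** Protocol 7.2.1.6 ends follow-up on the local read: "These visits are applicable for all patients unless locally CT-verified PD occurs", and "In case of PD this visit should be considered the End-of-Study Visit". Protocol 10.4.3 bases the endpoints, ORR and PFS among them, on the central read.

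**Duration.** SAP 6.3.6 computes duration of response "as the date of the first occurrence of PD or death minus the date at which the CR or PR was first observed", plus one day. The next sentence is a fallback: patients with no PD or death after the response contribute time to their last tumor assessment. Duration of clinical benefit has a parallel fallback. Duration of stable disease has none.

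**Before protocol version 4.0.** SAP 4.1 says of that design: "Following this design intermediate risk subjects would only start sunitinib treatment after confirmed PD". For these patients protocol 10.2.2.2 sets the response baseline at the first imaging after nephrectomy and leaves the details to the SAP. SAP 6.3.6 gives a baseline rule for them under PFS, but no baseline or scoring window for ORR, DCR or the durations.

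**The concern.** The two documents use the same term, best overall response, with different end points. Where scans exist after a central PD, the SAP text lets a later SD or PR set the patient's category, and response needs no confirmation (protocol 10.2.2.2), so one scan is enough. SAP 6.3.6 would then give that patient a PFS event at the first central PD and also count the patient as disease control or response.

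ORR and DCR are compared between arms by a Cochran-Mantel-Haenszel test. How many scans follow a central PD depends on when the local reader calls PD, and the trial is open-label. The duration summaries are also exposed: if the first PD on record precedes the first response, a literal subtraction gives a negative number of days.

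**Working it through.** The documents give no ORR, DCR or duration figure to reproduce. The check applies the stated rules to example patients and then sizes the effect.

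**1. When can a scan follow PD?**
- Central PD is called before local PD. Scanning continues, because only local PD ends the visits.
- An intermediate-risk patient enrolled before version 4.0 had PD and then started sunitinib. The SAP window opens six weeks after sunitinib, hence after that PD.
- Stopping study drug for safety does not by itself create post-PD scans, since protocol 8.5 says of such patients: "They should return for all following visits and assessments until PD".

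**2. Example patients.** Central scans at weeks 6, 12 and 24 (days 42, 84, 168 from sunitinib start). Rules from protocol Table 4: PD is at least 20% and 5 mm above the smallest sum; PR is at least 30% below baseline. The lesion sums are illustrative, with a baseline of 100 mm; the third row is given by category only.

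| Central reads (sums, mm) | Best response, SAP text | Best response, stop at first PD | Duration, literal first PD (days) | Duration, fallback or PD after response (days) |
|---|---|---|---|---|
| PD, SD, SD (121, 115, 112) | SD | PD | Clinical benefit and stable disease: 42 − 84 + 1 = −41 | Clinical benefit by fallback: 168 − 84 + 1 = 85. Stable disease: no fallback |
| PD, SD, PR (121, 95, 65) | PR | PD | Response: 42 − 168 + 1 = −125 | Response by fallback: 168 − 168 + 1 = 1 |
| PD, PR, PD | PR | PD | Response and clinical benefit: 42 − 84 + 1 = −41 | Fallback does not apply; PD after response would give 168 − 84 + 1 = 85 |
| PR, PR, PD (65, 60, 75) | PR | PR | Response: 168 − 42 + 1 = 127 | 127 |
| SD, SD, PD (95, 92, 112) | SD | SD | Clinical benefit: 168 − 42 + 1 = 127 | 127 |

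The first three rows change category; the last two, where PD comes last, do not. With the fallback applied, a negative duration of response or clinical benefit needs a PD before the response and a PD or death after it. That sequence is plausible, because scanning ends at local PD and the last central read may then also be PD.

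**3. Weight of one patient.** About 90 patients at 2:1 gives about 60 and 30. One reclassified patient moves a rate by 100/60 = 1.7 points or 100/30 = 3.3 points. For an assumed 1 to 6 patients in an arm, the shift is 1.7 to 10.0 points (arm of 60) or 3.3 to 20.0 points (arm of 30). The denominators are sunitinib-exposed patients only, so the true weight per patient is somewhat larger.

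**4. How many patients?** The documents do not say. An illustrative simulation covers the central-before-local route only. It used 200,000 patients per scenario, scans at 6, 12, 24, 36, 48 and 60 weeks, independent local and central reader error with SD 5% to 12%, a 5% or 10% new-lesion risk per scan, and scanning stopped at local PD. Central PD preceded the last scan in 17% to 29% of patients. DCR rose by 0.2 to 2.4 points and ORR by about 0.1 at most. Applied to 90 patients, that is 0.002 × 90 = 0.2 to 0.024 × 90 = 2.2 patients for DCR and 0.001 × 90 = 0.1 for ORR. None of the input rates comes from the documents, so this is an order of magnitude. The pre-version-4.0 group is not included.

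**The case against.** The strongest reply has four parts.

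- **The end-of-study visit is set per patient.** In case of PD it moves up to the local PD visit, so the SAP window normally closes at local PD. A reader might infer that all scans to the end of the trial count whatever the disease does; the visit rules do not support that. PD from a persisting new lesion also stays PD under protocol Table 6. This stands, and it confines the point to the two routes above.
- **The protocol is not of one mind.** Its response-rate definition has no stop at PD, and the SAP's reference to RECIST 1.1 can be read as importing the stop. This stands in part. But the SAP builds ORR and DCR on best overall response, the term that does carry the stop, and a programmer will follow the explicit time window.
- **The fallback sentence shows that the intended PD is one after the response.** This largely stands. A reader might infer that every pre-version-4.0 responder gets a negative duration; that is wrong, because a responder with no later PD or death goes to last tumor assessment. The fallback does not reach the PD, PR, PD sequence or duration of stable disease.
- **The effect is small, and the endpoints are secondary in an unpowered, exploratory trial.** This stands. An imbalance between arms is possible in an open-label trial, but nothing in the documents shows one and none was simulated.

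**Conclusion.** The inconsistency is real but narrow. It has consequences only where central PD precedes local PD, and for intermediate-risk patients who started sunitinib after PD under versions before 4.0. There, SD or PR after PD can count as disease control or response despite an earlier PFS event, and some durations can be negative if the formula is coded literally.

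The likely size is a few patients at most for DCR and almost none for ORR. That rests on assumed reader error and new-lesion rates and leaves out the pre-version-4.0 group, whose number and responses the documents do not give. A reader might infer that the survival results are at risk; they are not, because OS and 18-month survival do not use these scans. The text is still worth correcting: it departs from a protocol definition in a compared endpoint, and the remedy is cheap.

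**What to change.** In SAP 6.3.6:

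1. Derive best overall response from centrally read scans after the applicable response baseline, up to and including the first central PD after that baseline.
2. In all three duration formulas, use the first PD or qualifying death **after** the first CR/PR (response), CR/PR/SD (clinical benefit) or SD (stable disease). Say which deaths qualify, and give stable disease the same fallback as the other two.
3. For pre-version-4.0 intermediate-risk patients, apply the protocol's baseline (first imaging after nephrectomy) and reconcile it with the window that opens six weeks after sunitinib. If PD came between the two, scoring to first PD closes before that window opens. The SAP should state how such patients are classified, so that they are not excluded by default.
4. Reconcile the protocol's best overall response with its response-rate definition, and say which one ORR and DCR use.

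The cost is a few sentences and one or two programming conditions. SAP 6.2 lets minor clarifications be recorded in the Pre-Analysis Review Form before database lock. The downside should be stated openly: DCR may come out slightly lower, and some pre-version-4.0 patients with PD before sunitinib may not count as responders.
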